Cover Page

Official Title: Continuous Glucose Monitoring (CGM) in Kidney-Transplanted Adults

NCT Number: 05352230

Date of document: 09/30/2024

Inclusion of Individuals Across the Lifespan

Individuals 18 years of age and older are eligible to participate in this study. We anticipate the majority of patients will be 45-65 years of age, as this is the average age of end-stage renal disease patients eligible for kidney transplant.

Individuals less than 18 years of age are not approved by the FDA to use the Freestyle Libre continuous glucose monitoring system.

[name] is an Endocrinologist that sees patients at the Kidney-Transplant Clinic at the UAB Comprehensive Transplant Institute. He and his study team are well equipped to work with individuals 18 years and older in the inpatient and outpatient clinics associated with the UAB Comprehensive Transplant Institute that are designed to accommodate the adult kidney transplant patient population from pre-op through outpatient recovery.

Inclusion of Women and Minorities

We plan to enroll a total of 30 participants.

Based on UAB Comprehensive Transplant Institute's reporting to the Scientific Registry of Transplant Recipients, 60% of kidney transplant recipients are male. Therefore, we anticipate participants will be 60% male (n=18) and 40% female (n=12). No sex/gender group will be excluded or targeted for enrollment in this study.

Based on UAB Comprehensive Transplant Institute's reporting to the Scientific Registry of Transplant Recipients, we anticipate participants will self-identify their race/ethnicity according to the following percentages: 63% African American (n=19), 32% Caucasian (n=10) and 4% Hispanic/Latino (n=1). However, no racial or ethnic group will be excluded or targeted for enrollment in this study.

Recruitment and Retention Plan

Recruitment:

The proposed pilot study plans to enroll 30 end-stage renal disease patients awaiting kidney transplant at the Kidney-Transplant Clinic that is part of the UAB Comprehensive Transplant Institute.

To facilitate recruitment, our team plans to leverage UAB's electronic medical record system/reporting, as well as routine care plans and coordinators. Specifically, the study team will identify potential participants by querying UAB's electronic medical record. Using that information, the study team will supply patients on the kidney transplant waiting list letters with information about the study. Patients admitted to the hospital to receive a kidney transplant will also be directly contacted about the study.

Retention:

To minimize the burden of study participation, we integrated study activities with routine care plans and coordinators. Planned study activities coincide with standard post-kidney transplant care plans. Kidney transplant coordinators facilitate post-kidney transplant standard of care.

STUDY TIMELINE

[Home](#) > [Search for Applications](#) > [Application Information](#) > [Component Information](#)

Actions

[RETURN TO SUMMARY](#)

Component Type

Overall

— Miscellaneous

• 51 • 11

 [Show Help](#)

Miscellaneous

Summary

HSCT Post
Submission

[Human Subjects Summary](#) > [Study Record: 5](#) > Inclusion Enrollment Report: 1

Inclusion Enrollment Report 1 v1.0 

OMB Number: 0925-0770

Expiration Date: 09/30/2024

* 1. Inclusion Enrollment Report Title	Continuous Glucose Monitoring (CGM) in Kidney-Transplanted Adults
* 2. Using an Existing Dataset or Resource	 Yes  No
* 3. Enrollment Location Type	 Domestic  Foreign
4. Enrollment Country(ies)	UNITED STATES OF AMERICA
5. Enrollment Location(s)	Hospital

Planned

	Ethnic Categories								
	Not Hispanic or Latino				Hispanic or Latino				Total
Racial Categories	Female		Male		Female		Male		
American Indian/Alaska Native		0		0	0	0		0	0
Asian		0		0	0	0		0	0
Native Hawaiian or Other Pacific Islander		0		0	0	0		0	0
Black or African American		7		12	0			0	19
White		3		7	0			1	11
More than One Race		0		0	0			0	0
Total		10		19	0			1	30

Cumulative (Actual)

		Ethnic Categories									
		Not Hispanic or Latino			Hispanic or Latino			Unknown/Not Reported Ethnicity			Total
Racial Categories	Female	Male	Unknown/Not Reported	Female	Male	Unknown/Not Reported	Female	Male	Unknown/Not Reported		
	Black or African American	0	0	0	0	0	0	0	0	0	
White	0	0	0	0	0	0	0	0	0	0	
More than One Race	0	0	0	0	0	0	0	0	0	0	
Unknown or Not Reported	0	0	0	0	0	0	0	0	0	0	
Total	0	0	0	0	0	0	0	0	0	0	

Instructions for Participant Level Data Upload

Participant level data file (CSV):

[Download Participant Level Data Template](#)

© 2022 NIH. All Rights Reserved. | Screen Rendered: 06/14/2022 11:26:27 EDT | Screen Id: ASSIST0090@6211 | Version: 2.53.00.039

[Contact Us](#) [Help Desk](#) [Privacy Notice](#) [Accessibility](#) [Disclaimer](#)

[HHS Vulnerability Disclosure](#)

Protection of Human Subjects

1. Risks to Human Subjects

a. Human Subjects Involvement, Characteristics, and Design

The primary outcome of this study is assessment of the feasibility and acceptance of CGM usage in the post-operative kidney transplant population (e.g. quality-of-life). Secondary outcomes will estimate if CGM usage improves post-operative diabetes management (e.g. time in range). The study is a randomized, open-label, cross-over clinical trial consisting of two study arms where participation will last eight months. A permuted block randomization list, block sizes varying from 2 to 6, will be developed to randomly assign subjects to treatment sequence (CGM followed by glucometers, or glucometers followed by CGM). We plan to enroll 30 post-operative kidney-transplant diabetics.

Inclusion Criteria:

- Age \geq 18 years
- History of diabetes diagnosis (Type 1, Type 2, or atypical) prior to kidney transplant
- Current treatment for diabetes includes at least one daily injection of long-lasting insulin
- Able to read and understand English
- Able to consent for themselves

Exclusion Criteria:

- Age $<$ 18 years
- History of kidney and/or pancreas transplant
- Has used CGM in the past
- Mental or psychiatric conditions that would preclude continuation in the study
- Unable to read or understand English
- Unable to consent for themselves

b. Study Procedures, Materials and Potential Risks

Study Procedures and Materials:

Eligible participants will engage study staff during regularly scheduled, standard of care, visits. The first (i.e. baseline) visit is one day post-operative surgery. Participants will be randomized to one of two groups. Group 1 participants (n=15) will receive a Freestyle Libre continuous glucose monitor (CGM) that reports glucose levels to participants every 15 minutes for twelve weeks. Group 2 participants (n=15) will receive a glucometer for self-management of their diabetes as per the standard of care for twelve weeks. Halfway through the study (week 12 post-operative surgery), all participants will use a glucometer to manage their diabetes eight weeks, which serves as a washout period. At week 20 post-operative surgery, Group 2 participants will receive a CGM to use for twelve weeks, and Group 1 will continue using a glucometer for twelve weeks. The study will conclude at week 32 post-operative surgery visit.

Participants managing their diabetes with glucometers during the first and last twelve weeks of the study (Groups 2 and 1 respectively) as well as Group 2 during weeks 18-20 of the study will use a Freestyle Libre "Pro" CGM, which collects glucose information in the same manner as the CGM described above but reporting not provided to participants and is accessible to the study team via remote monitoring.

At regularly scheduled post-operative visits on weeks 2, 12, 20 and 32, the study team will request participants to complete two quality-of-life surveys (Diabetes Treatment Satisfaction Questionnaire (DSTQ) and Hypoglycemic Confidence Scale (HCS)) and record glucose readings from the CGM and/or glucometers. Participants' medical records will be leveraged to assess surgical outcomes, diabetes management and related clinical information (e.g. clinical labs, kidney biopsies).

Potential Risks:

Glucose monitoring related pain, discomfort and Infection: Sensor insertion and finger-prick based glucose readings may cause temporary pain, bleeding and/or bruising at the site of insertion. Moderate to severe itching, reddening and/or scaling of the skin, rash and/or bleeding are infrequent risks associated with wearing the sensor. A infrequent risk is sensor breakage, which can require sensor tip extraction via tweezer.

Group Assignment: Participants are assigned to a group by chance, which may prove to be less effective or have more side effects than the other study group or alternatives.

Confidentiality: A breach of confidentiality may impact participants psychologically and could influence insurance and/or employers decisions based on study purpose, participant enrollment or health status. This risk is minimal.

2. Adequacy of Protection Against Risks

a. **Informed Consent:**

As approved by the UAB IRB, a HIPAA waiver will be utilized for all participants strictly for recruitment and screening purposes. A trained study team member will provide an IRB approved consent form to interested individuals likely meeting the inclusion/exclusion criteria. Such individuals will have access to it for more than 24 hours before the study team member reviews the consent form with the individual and answers any questions. The study personnel will explain the potential risks and benefits. Study team members will clarify that participants may refuse to answer any study questions without jeopardizing their continued enrollment in the study and that election to enroll or not enroll will not influence their care or future interactions with the institution. The signed informed consent form will be retained by the study team and a copy will be made available to the participant.

b. **Protections Against Risk:**

Glucose monitoring related pain, discomfort and Infection: Study team members and participants will take precautions to avoid infections at the site of finger pricking and sensor insertion (e.g. wearing gloves, washing hands and/or cleaning the skin with alcohol prior to pricks/insertion). Participants will be directed to contact study team staff if they notice any adverse reactions to wearing the sensor. If the sensor breaks, participants will be instructed to remove the sensor with tweezers and notify the staff.

Group Assignment: Participants are assigned to a group by chance, which may prove to be less effective or have more side effects than the other study group or alternatives. However, this risk is not greater than the standard of care.

Confidentiality: The University of Alabama at Birmingham regularly reviews its policies and procedures regarding the confidentiality of its study subjects. All staff receives training on the importance of maintaining confidentiality. Strict confidentiality will be maintained to the fullest extent by the research team. Hardcopy information will be kept in a secure, locked cabinet with limited access. Digital information will be stored in a HIPAA compliant, password protected database with limited access to authorized study personnel. Data are stored and analyzed according to subject identification numbers, and in no instances are subjects' names or other identifying information available in publically accessible files or in published material. The study consent form will inform participants that not sharing information about their participation in this study with others will minimize breach of confidentiality risks.

c. **Vulnerable Subjects**

The proposed study does not involve vulnerable subjects.

3. Potential Benefits of the Proposed Research to Research Participants and Others

Participants may benefit from this study by obtaining additional health information made available by continuous glucose monitors. The results of this study are expected to inform the acceptability and feasibility of continuous glucose monitoring among diabetics after kidney transplantation and estimate if continuous glucose monitoring improves glucose control among diabetic kidney transplant recipients.

4. Importance of Knowledge to be Gained

Diabetes is the largest risk factor for end-stage renal disease and kidney transplant rejection. The less glucose levels are controlled the more likely transplanted organs are to fail. Therefore, if continuous glucose monitoring improves glucose control in diabetic kidney transplant recipients, we anticipate to see a reduction in kidney transplant failure rates. This finding may benefit outcomes among other solid-organ transplant populations, as well as policies related to insurance coverage of continuous glucose monitoring in solid-organ transplant populations.

Data and Safety Monitoring Plan

Monitoring Responsibility:

Data and Safety Monitoring is the responsibility of the study director, [name].

Adverse Event (AE) Management:

Expected Events: Adverse events include expected side effects of a serious nature or unexpected side effects/events, regardless of severity. All potential risks, as well as protections against those risks, are detailed in the "Protection of Human Subjects" document, the human subjects protocol and the informed consent document.

Frequency: Adverse event information will be collected during each standard of care clinic visit. In addition, participants will be instructed to report adverse events as they occur to the study director, whose contact information is provided in the informed consent. Throughout the study, the study director will be available to address subject related medical questions and to ensure subject safety.

Actions: As needed, the study director will refer participants to the appropriate medical care (e.g. urgent care or non-urgent care). In cases of emergency, participants will be instructed to call 911. Should a participant require urgent or emergency care, the study director will follow up with the participants' healthcare providers to determine whether it is safe for the participant to continue in the trial. Should an adverse event occur while the participant is being seen at UAB, study related injuries will be promptly addressed and treated using resources available at UAB.

Documentation: Adverse events will be documented on specialized case report forms and graded on their attribution (unrelated to the protocol, or possibly, probably or definitely related to the protocol), severity (mild, moderate, severe), expectedness (unexpected versus expected) and frequency. We will also document any actions taken related to the adverse event and the outcome or resolution of the event.

Reporting: All adverse events will be reported to the UAB IRB with a description of the event, when and how it was reported, and appropriate documentation to corroborate the event on case report forms. A summary of all adverse events are reported as part of the IRB protocol Continuing Review. Serious Adverse Events (SAE) will be reported by the study director to the IRB no later than five business days after the event. Non-serious, unexpected adverse events that are related or possibly related to the study will be reported to the IRB within 10 business days of the event. The IRB will have the responsibility to confirm the severity of the adverse event, determine if it is likely that the adverse event was related to the study and make recommendations for continuation, modification or cessation of the study.

Data Monitoring Management:

[name] will review the quality and accuracy of all data collected during the study. Protection of data from a breach of confidentiality is described in the Protection of Human Subjects document.

Statistical Design and Power

A permuted block randomization list, block sizes varying from 2 to 6, will be developed to randomly assign subjects to treatment sequence (CGM followed by glucometers, or glucometers followed by CGM). 66 individuals would be required to achieve 80% statistical power in this crossover design for a medium effect size of 0.5 using a two-tailed Type I error of 0.05. Given we have only one year to conduct the pilot, we believe a sample size of 30 is the highest number of individuals that can be recruited and studied within that period. We will include 15 patients in each group. One group will receive CGM and the other will use glucometers for glucose monitoring. The only way this sample size could achieve adequate statistical power is that the difference in interventions generates a very large effect size (>0.8). We do not anticipate effect sizes that large and believe the smallest clinically relevant effect sizes would be in the range 0.2 to 0.5. Therefore, this study is unlikely to generate adequate statistical power. However, achieving statistical power is not the objective of a pilot study. The objective is to demonstrate the feasibility of recruiting individuals to the study, demonstrating that individuals will complete the study, demonstrating that clean and usable data can be collected, and examination of that data provides preliminary evidence of an effect in the direction anticipated. Therefore, the criteria for evaluating this pilot are that a) 80% of all individuals recruited will agree to randomization and complete the study with usable data and b) adequate evidence is observed in the direction anticipated. If we observe a test statistic for treatment effect difference greater than or equal to 1.055 with 28 degrees of freedom, which equates to effect size an effect size of 0.275, we will consider this as adequate statistical evidence to proceed. Such an approach equates to conducting the analysis with a one-tailed Type I error rate of 0.15. If both criteria are met (rate of completion and preliminary data provides evidence in direction anticipated), we will utilize the data collected to design a larger randomized controlled trial. If the criteria are not met, we will refine protocol and data collection procedures.

Dissemination Plan

As Principal Investigator for this study, I will comply with the NIH Policy on the Dissemination of NIH-Funded Clinical Trial Information in NIH Guide Notice NOT-OD-16-149. The proposed study title is Continuous Glucose Monitoring (CGM) in Kidney-Transplanted Adults" and is currently registered on ClinicalTrials.gov (NCT05352230). As PI, I will be responsible for ensuring that the information in the clinical trial record is updated at least once every 12 months and I will ensure that results are reported no later than one year after the clinical trial primary completion date.

The consent form for this clinical trial will contain language specifying that the study is registered at clinicaltrials.gov. The required wording on all consent forms by the University of Alabama at Birmingham (UAB) Institutional Review Board for Human Use is:

"A description of this clinical trial will be available on <http://www.ClinicalTrials.gov>, as required by U.S. Law. This website will not include information that can identify you. At most, the website will include a summary of the results. You can search this website at any time."

The Center for Clinical and Translational Science (CCTS) works with investigators to provide education and assistance to meet the requirements of ClinicalTrials.gov for registration and reporting as specified in the NIH Policy on the Dissemination of NIH-Funded Clinical Trial Information (NOT-OD-16-149). The CCTS maintains a web site (<https://www.uab.edu/ccts/clinical-translation/clinical-services/crsp/study-start-up/regulatory-issues/clinicaltrials-gov>) specifically for the purpose of updating investigators regarding changes to ClinicalTrials.gov. The CCTS provides consultations and one-on-one training to assist investigators in initiating and maintaining their ClinicalTrials.gov entry.

Description of the availability of Investigational Product (IP) and Investigational New Drug (IND) or Investigational Device Exemption (IDE) status:

The Freestyle Libre 2 and Freestyle Libre Pro are FDA-regulated test articles, legally marketed in the United States (FDA Letters K193371 and P150021, respectively) when used in accordance with their labeling for continuous glucose monitoring (CGM). Therefore, these devices are no longer investigation as they have been approved for marketing and commercial distribution in the United States. This study will use devices in accordance with their labels.

All components of the device will be stored securely (behind a locked door) in the principal investigator's office in [name]. All floors above 6 in FOT are badge-protected. Only qualified research staff will have access to the office where the devices are stored. The devices will be inserted for two weeks at the beginning and end of Phase I or Phase II, dependent on group assignment. The participation will only wear the sensor for the Pro version of the device and data will be collected remotely from the device. Participants will be instructed to discard the sensor after each two week period of monitoring is complete.

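### Does the go criterion (t at least 1.055, 28 df, one-tailed 15%) fail because it names no outcome or time window?

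*Combined protocol and SAP*

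**What the plan says.** *Statistical Design and Power* sets two criteria for going on to a larger trial: (a) 80% of those recruited accept randomisation and complete with usable data, and (b) adequate evidence in the anticipated direction. For (b) the rule is "If we observe a test statistic for treatment effect difference greater than or equal to 1.055 with 28 degrees of freedom", said to correspond to an effect size of 0.275, and "Such an approach equates to conducting the analysis with a one-tailed Type I error rate of 0.15". The same text appears in the IRB application under *Target Accrual Information*. Both criteria must be met; otherwise procedures are refined.

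The outcomes are described elsewhere. *Protection of Human Subjects*, 1a, gives the primary outcome as "assessment of the feasibility and acceptance of CGM usage in the post-operative kidney transplant population (e.g. quality-of-life") and adds "Secondary outcomes will estimate if CGM usage improves post-operative diabetes management (e.g. time in range"). Under *Study Procedures and Materials*, "At regularly scheduled post-operative visits on weeks 2, 12, 20 and 32, the study team will request participants to complete two quality-of-life surveys"; the visit list in the IRB application's Methods adds a baseline administration. The *Data collection variables* list has seven sensor glucose measures: time in range, time above 180, below 70 and below 54 mg/dL, mean glucose, variability and GMI.

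**The concern.** A numerical cut-off needs a variable, and criterion (b) has none. Quality of life and time in range are each introduced only as examples. The two questionnaires are not ranked and are given at several visits, and there is no rule for results that disagree. In an open-label trial, two analysts following the text could reach opposite verdicts on the same data. If the outcome were picked after seeing results, the 15% would no longer describe the rule applied. The consequence would be a larger trial launched, or held back, on a criterion that was not truly fixed in advance.

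**Working it through.** **Inputs.** From *Statistical Design and Power*: t = 1.055, 28 df, one-tailed 0.15, effect size 0.275, N = 30 (15 per sequence), and 66 participants for 80% power at effect size 0.5 with two-tailed 0.05. The documents give no correlation between outcomes, so a range is assumed below.

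**1. The plan's own figures.**
- Error: P(T28 ≥ 1.055) = 0.1502. The exact 15% point is 1.0560.
- Scale: t = d × √(N/2), the crossover t-test with zero within-person correlation. At N = 66 the noncentrality is 0.5 × √33 = 2.87 and power is 80.8%; N = 64 gives 79.5%. The plan's 66 is reproduced.
- Effect size at the cut-off: 1.055 × √(2/30) = 0.272, against the stated 0.275. The gap is immaterial: 0.275 corresponds to t = 1.065 and an error of 0.148.

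**2. Drop-out.** With 80% of 30 completing, N = 24 and df = 22. P(T22 ≥ 1.055) = 0.151, and the effect size at the cut-off is 1.055 × √(2/24) = 0.305. The error barely moves.

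**3. What if more than one outcome could count?** For two independent tests, either passing has probability 1 − 0.85² = 0.278 and both passing 0.15² = 0.023. Simulation of two correlated outcomes (15 + 15 patients, t-test on within-patient period differences, 400,000 runs per cell, no true effect) gives:

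| Rule for (b) | correlation 0 | 0.5 | 0.7 |
|---|---|---|---|
| One outcome fixed in advance | 0.150 | 0.150 | 0.150 |
| Either may count | 0.278 | 0.244 | 0.222 |
| Both must pass | 0.022 | 0.058 | 0.078 |
| Opposite verdicts | 0.255 | 0.187 | 0.144 |

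The first row is the nominal rate. If any one of the seven sensor metrics were enough, the rate would be 1 − 0.85⁷ = 0.68 if independent, and 0.27 at correlation 0.9. The second and third rows, and the seven-metric figure, need a combination rule that the plan does not contain.

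**4. Does disagreement between outcomes show a fault?** Take a true effect of 0.5 on one questionnaire and none on the other, uncorrelated. A single test passes with probability 0.811 at effect 0.5 and 0.15 at zero.
- Affected score passes, unaffected fails: 0.811 × 0.85 = 0.689.
- The reverse: 0.189 × 0.15 = 0.028.

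Opposite verdicts total about 72%, but nearly all of that is the test telling the two outcomes apart correctly. Naming one outcome would not lower the rate; it would only say which verdict counts.

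**5. How open is the window once an outcome is chosen?** For the questionnaires, week 2 has no Phase II counterpart, so the matching on-treatment visits are weeks 12 and 32. For sensor data, the visit list gives control-arm recordings that match across phases only in weeks 0-2 and 20-22. Choosing the outcome therefore largely settles the window.

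**The case for a change.** The strongest case for a change is that (b) is one of two formal criteria and cannot be applied without a choice that the text leaves open. Reading it as the primary outcome does not yield a single test, because quality of life is only an example and has two scales. The stated purpose in the IRB application adds microalbuminuria and subclinical rejection, and the anticipated direction differs by metric. Naming an outcome would take a few sentences and no extra patients or visits.

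Much of this stands as description: the outcome is not named in the documents available. It does not follow that the 15% is wrong. The criterion speaks of one statistic and one analysis, and for that the figure is right. Any rewrite would also leave the key entries for the sponsor to fill, and the choice is a real one. A questionnaire fits the primary example, whereas the IRB application's Background says the larger trial would examine hyperglycaemia and graft survival. The grant application and schedule of events are listed as attachments but were not available, and either may settle the matter.

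The control-sensor timing is a genuine but separate inconsistency. *Study Procedures and Materials* has a sentence beginning "Participants managing their diabetes with glucometers during the first and last twelve weeks of the study (Groups 2 and 1 respectively") that describes wear over those weeks, plus a Group 2 wear in weeks 18-20 that the visit list lacks. The device-availability section says "The devices will be inserted for two weeks at the beginning and end of Phase I or Phase II, dependent on group assignment". The visit list puts the last control fittings at weeks 12 and 32, so they would record after the phase has ended. These passages must be reconciled, but they bear on (b) only if a sensor metric is used. The early window has its own limitation, since "The first (i.e. baseline) visit is one day post-operative surgery".

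**Conclusion.** No change to the plan follows. Criterion (b) lacks a named outcome and window, but this is detail that an analyst supplies by fixing one outcome, its scoring, one window per phase and the expected direction before any outcome data are analysed. The other outcomes are then descriptive. On that reading the stated 15% is correct (0.1502 at 30 completers, 0.151 at 24), and the effect size of 0.275 is right to within 0.003.

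The 22-28% figure assumes that either of two questionnaires may satisfy (b), with correlation between 0.7 and 0; nothing in the plan says so. Progression also requires (a), so the overall chance of a false go cannot exceed that of (b) alone. The plan disclaims adequate power and makes no efficacy claim, and failing (b) leads only to refining procedures. The conclusion depends on the choice being made before results are seen. If several outcomes were tried and the best one kept, the 15% would no longer apply.

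### Does the pilot's go threshold of 0.275 contradict the plan's own statement that effects from 0.2 upward may be clinically relevant?

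*Combined protocol and SAP*

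**What the plan says.** The Statistical Design and Power section and the Target Accrual Information text of the IRB application (section 9, Prospective) carry the same paragraph on this point.

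- Full-power reference: "66 individuals would be required to achieve 80% statistical power in this crossover design for a medium effect size of 0.5", at a two-tailed 0.05.
- Relevance: the investigators "believe the smallest clinically relevant effect sizes would be in the range 0.2 to 0.5". They say openly that 30 people will probably not give adequate power, and that power is not what a pilot is for.
- Go criterion (b): a test statistic of at least 1.055 on 28 degrees of freedom, "which equates to effect size an effect size of 0.275, we will consider this as adequate statistical evidence to proceed".
- Error rate: "Such an approach equates to conducting the analysis with a one-tailed Type I error rate of 0.15".
- Consequences: if (b) and the 80% completion criterion (a) are both met, "we will utilize the data collected to design a larger randomized controlled trial". Otherwise, "If the criteria are not met, we will refine protocol and data collection procedures".

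Protection of Human Subjects, section 1a, sets the pilot's purpose: "The primary outcome of this study is assessment of the feasibility and acceptance of CGM usage". Whether CGM improves diabetes management is listed there as secondary.

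**The concern.** The two numbers stand a few sentences apart on what appears to be the same scale. An observed effect of 0.20 to 0.27 could be called relevant under one sentence and inadequate under another. The plan gives the rule's false-pass rate (0.15) but not its miss rate, and that rate is high at the bottom of the range.

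If this were a real inconsistency, two things would be at stake. A pilot with good completion and clean data could be sent back for refinement because of sampling error. A pilot that passed would tend to overstate the effect, and a larger trial sized on that estimate would be too small.

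**Working it through.** **Inputs**, all from Statistical Design and Power: cut 1.055 on 28 df; effect at the cut 0.275; one-tailed 0.15; N = 30 (15 per sequence); 66 people for 80% power at 0.5, two-tailed 0.05; relevant range 0.2 to 0.5.

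**1. Find the effect-size scale.** The plan does not name it. In a two-sequence crossover with the effect in within-person standard deviations, SE = √(2/N), with N − 2 df.

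- N = 66: SE = √(2/66) = 0.174 and noncentrality 0.5/0.174 = 2.87, giving power 80.8%. The smallest N reaching 80% is 65, or 66 as an even number. This matches the plan.
- N = 30: SE = √(2/30) = 0.2582. The cut is 1.055 × 0.2582 = 0.272, against the stated 0.275.
- N = 30, true effect 0.8, two-tailed 0.05: power 85%. This fits the plan's remark that only a very large effect would be adequately powered.

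Two other scales fail. Standard deviation of the paired difference gives 34 people and a cut of 0.193. A parallel-group scale gives 128 people and a cut of 0.385.

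**2. Check the error rate.** P(T ≥ 1.055) on 28 df is 0.1502. The 0.85 quantile is 1.056. The stated 0.15 is right.

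**3. Pass and fail rates of criterion (b).** Noncentral t, 28 df, noncentrality = d/0.2582, one outcome fixed in advance:

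| True effect d | Noncentrality | Pass | Fail |
|---|---|---|---|
| 0 | 0 | 15% | 85% |
| 0.2 | 0.77 | 39% | 61% |
| 0.3 | 1.16 | 55% | 45% |
| 0.4 | 1.55 | 69% | 31% |
| 0.5 | 1.94 | 81% | 19% |

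The trapezoidal average of the failure rate over 0.2 to 0.5 is (0.606/2 + 0.454 + 0.309 + 0.189/2)/3 = 0.387, about 39%. With 24 completers (80% of 30; 22 df), the rule fails 64% of the time at 0.2 and 25% at 0.5.

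**4. Set the two statements side by side.** The range 0.2 to 0.5 describes true effects that would matter. The plan does not commit to 0.2 as the single smallest one, and 0.2 < 0.275 < 0.5. The cut of 0.275 is a demand on an estimate whose standard error is about 0.26, and it is set by the chosen one-tailed 0.15. Relevance and strength of evidence are different questions. An observed 0.22 can be of relevant size and still be weak evidence that the effect is not zero. Nor is the 61% at 0.2 a malfunction: a perfectly precise estimate of 0.2 would also fall below 0.275, so failing is the expected result there.

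**5. Selection among passing pilots.** If the true effect is 0.2, the mean estimate among pilots that pass is 0.45 (simulation). A crossover sized on 0.45 would have 80 people and 24% power at 0.2, where 396 are needed for 80%. This would hurt only if the next trial were sized on the pilot's point estimate. The plan says the data will inform the design of that trial, which could equally mean variability, completion or feasibility.

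**6. Would another rule be plainly better?** Take three zones: proceed at or above the cut, inconclusive between zero and the cut, refine below zero. With no true effect, 15% of pilots proceed and 35% are inconclusive, so up to 50% could go forward against 15% now. At a true 0.2 the split is 39% proceed, 39% inconclusive and 22% refine. The gain in sensitivity is paid for in false passes, and the middle zone would still need a decision rule.

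**The case for a change.** The strongest opposing argument is that the plan's admission of low power concerns the conventional two-tailed 0.05 test. It then brings in a different rule, makes it a condition for proceeding, and gives only its false-pass rate. If power is not the aim of a pilot, a test-statistic cut arguably should not be mandatory, and refining procedures does not cure a miss caused by chance. Even a true effect of 0.275 fails about half the time (49%).

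Two parts of this stand. The plan does not tabulate pass rates for criterion (b), and those rates are modest at the lower end of its range. But they follow directly from figures the plan does give, and printing them would change no result. The looser one-tailed 0.15 is itself the response to the small sample: it gives about 80% power at the medium effect of 0.5 with the 30 people available. Someone who wanted good sensitivity at 0.2 would need far more people; holding both errors at 15% takes 216. The plan never claims that sensitivity. Failing does not rule out a later trial.

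**Conclusion.** There is no contradiction and no wrong figure. The 66, the 0.275 (0.272 recomputed) and the 0.15 (0.1502) agree with one another, the threshold lies inside the stated range of relevant effects, and the limited power is disclosed. The 61% miss rate at a true effect of 0.2 is real, but it is the worst point of that range. It falls to 19% at 0.5 and averages about 39% between them.

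These percentages rest on three assumptions: 30 analysed participants, one outcome fixed beforehand, and the within-person scale. The plan does not state which outcome and visit criterion (b) tests, so the percentages describe the rule once an outcome is fixed; that is a separate question of wording. The scale is inferred, but of the three tried it is the only one that reproduces both 66 and roughly 0.275. On the others, the miss rate at 0.2 would be 48% (paired difference) or 69% (parallel groups). The conclusion does not depend on which applies. No change is called for on this point.
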